## Sample Collection/Analysis

You indicated on the "Type of Research" page that your study involves a sample (specimen) collection and/or analysis.

1 \* What type of samples will be involved in this study? (Check all that apply)

Prospective (will be collected)  
 Existing (previously collected at the time of initial IRB submission)

2 \* Will genetic analysis/testing be done on any of the samples?

Yes  No

3 \* Will this study involve banking of samples (storing for future research use)?

Yes  No

4 \* What is the purpose of the sample collection and/or analysis?

The purpose of the sample collection is to culture and determine bacterial colonization or immune response as a proxy for biofilm formation.

5 \* Is there the possibility that cell lines will be developed with any of the samples?

Yes  No

6 \* Will the samples be released to anyone not listed as an investigator on the protocol?

Yes  No

6.1 If Yes, give name(s) and affiliation(s):

7 \* Will the sample material be sold or given to any third parties?

Yes  No

7.1 If Yes, give name(s) and address(es):

ID: VIEW4E0E1A4B80000  
Name: v2\_Sample Collection/Analysis

## Prospective Samples

You indicated that the study involves collection of prospective samples (specimens).

1 \* What type of sample will be collected? (Check all that apply)

Blood  
 Bone Marrow Aspirate/Biopsy  
 Cerebrospinal Fluid  
 Saliva  
 Skin  
 Sputum  
 Stool  
 Tissue  
 Tumor  
 Urine  
 Other

1.1 If Other, specify:

2 For blood draws, specify the amount drawn, in teaspoons, at each visit and across the course of the subject's entire participation time:

Blood draws are routinely taken throughout a patient's follow-up to monitor their health. We plan to take up to three blood draws, with the use of an indwelling catheter when available, to culture for research purposes during their hospitalization for diagnosed surgical site infection.

Patients will be identified at random in the orthopaedic trauma clinic and current admitted patients who have been diagnosed with an infection. Once eligibility has been confirmed, the informed consent process will be completed by the Research Coordinator and the attending surgeon. Patients will be approached about potential participation in the study as soon as is feasible following determination of eligibility.

Once consented into the study, baseline data regarding participant characteristics, injury characteristics, fracture classification and medical history/co-morbidities will be collected. Characteristics about hospital course and treatment received will also be collected (i.e. blood culture results, antibiotic usage, etc).

At each follow up visit, participants will undergo a clinical evaluation by the treating surgeon as part of standard of care following any surgical procedure and will be interviewed by the research coordinator. Blood draws will be taken at the initial and each subsequent visit and will be analyzed in the laboratory of one of the investigators in the study. If the patient is currently infected currently, or become infected at any point in the future, additional blood draws may be taken, at a maximum of 10 draws, over the period of two years from the clinical diagnosis of infection. The amount of blood that is drawn will not exceed 50 ml or 3 ml per kg in a 8 week period, and collection may not occur more frequently than 2 times per week.

Finally, we would prospectively correlate the laboratory findings with clinical findings by searching the patients' medical records to find outcomes such as a biofilm formation.

3 \* What type of samples will be collected? (Check all that apply)

- Leftover samples that were obtained for clinical purposes (no additional research procedures required)
- Samples obtained specifically for research purposes-additional taken during a clinical procedure
- Commercial (for profit) samples
- Samples obtained specifically for research purposes-obtained via a separate collection procedure done solely for the purposes of the study
- Other

3.1 If Other, specify:

4 \* How are these samples labeled? For example, do they contain name, initials, dates, Social Security number, medical record number, or other unique code?

Unique code for each patient such that the samples will be blinded from obvious patient identifiers.

5 \* Will sample(s) be made available to the research subject (or his/her medical doctor) for other testing?

- Yes
- No

6 \* If a participant withdraws from the study, will that participant have the option to get the remaining portion of their sample(s) back?

- Yes
- No

7 \* If the participant withdraws, explain how their sample(s) will be handled (For example, will sample(s) be destroyed, anonymized, etc.):

Samples will be held anonymously if the patient withdraws until analysis is complete.

8 \* Will the samples be destroyed after the study is over?

- Yes
- No

8.1 If No, describe how the samples will be stored, where they will be stored, and for how long.

The samples will be stored in a freezer at [name] lab until deemed no longer useful.

ID: VIEW4E0E257D60C00  
Name: v2\_Prospective Samples

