## Study Procedures

**If you uploaded a separate research protocol document in the 'Research Protocol' page, cite the applicable section and page numbers from that document in the answer boxes below. (If this study is a collaborative UM/VA study please list each procedure that is being conducted and the locations where it is being conducted.)**

1 \* Describe all procedures being performed for research purposes only (these procedures would not be done if individuals were not in the study) and when they are performed, including procedures being performed to monitor subjects for safety or to minimize risks:

Patients will be identified at random in the orthopaedic trauma clinic and current admitted patients who have been diagnosed with an infection. Once eligibility has been confirmed, the informed consent process will be completed by the Research Coordinator and the attending surgeon. Patients will be approached about potential participation in the study as soon as is feasible following determination of eligibility.

Once consented into the study, baseline data regarding participant characteristics, injury characteristics, fracture classification and medical history/co-morbidities will be collected. Characteristics about hospital course and treatment received will also be collected (i.e. blood culture results, antibiotic usage, etc).

At each follow up visit, participants will undergo a clinical evaluation by the treating surgeon as part of standard of care following any surgical procedure and will be interviewed by the research coordinator. Blood draws will be taken at the initial and each subsequent visit and will be analyzed in the laboratory of one of the investigators in the study. If the patient is currently infected currently, or become infected at any point in the future, additional blood draws may be taken, at a maximum of 10 draws, over the period of two years from the clinical diagnosis of infection. The amount of blood that is drawn will not exceed 50 ml or 3 ml per kg in a 8 week period, and collection may not occur more frequently than 2 times per week.

Finally, we would prospectively correlate the laboratory findings with clinical findings by searching the patients' medical records to find outcomes such as a biofilm formation.

2 \* Describe all procedures already being performed for diagnostic or treatment purposes (if not applicable to the study, enter "N/A"):

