As part of the routine standard of care for any patient readmitted to the hospital for suspected surgical site infection cultures are obtained and sent for laboratory analysis to confirm bacterial colonization. As this is an assay to identify earlier a surgical site infection, this would be done earlier than any current testing.

3 \* Describe the duration of an individual participant's participation in the study:

Following index clinic blood draws, patients will be followed during their regularly scheduled visits with their surgeon to assess wound healing.

4 \* Describe the amount of time it will take to complete the entire study:

The study will last 1-2 years in total.

5 \* Describe any additional participant requirements:

There are no additional requirements.

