**Number Criteria**

View 1	Previous fracture fixation with an implant (intramedullary nail, plate, screws), or joint revisions, or periprosthetic fracture, or admitted from orthopaedic trauma clinic due to infection, or inpatient with a known infection.
View 2	Age 18 and older
View 3	English speaking

List exclusion criteria (List each Exclusion Criteria individually, using the ADD button):

Number	Criteria
View 1	Patients with planned follow-up at another medical center
View 2	Patient lives outside of the hospital catchment area

After entering the inclusion and exclusion criteria above, click the Save link. CICERO will automatically generate a printable Eligibility Checklist for you to use in your research. To review the checklist, click on the resulting link below. This checklist is also available under the Documents tab of this application.

Eligibility Checklist for HP-00055743\_7 v10-6-2015-1444148031816(0.01)

ID: VIEW4E0E5185F9000  
Name: v2\_Eligibility

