## Recruitment

1 \* Describe plans for recruitment, including the identification of potential participants (or acquisition of charts/records/samples) and initial interactions with them: (If this study involves the VA please list all sites at which recruitment will take place.):  
All orthopaedic patients over age 18 attending a follow-up visit with an attending orthopaedic traumatologist will be eligible. Patients over the age of 18 admitted directly from the orthopaedic trauma clinic will be eligible. Current patients over the age of 18 that have been diagnosed with an infection. Once eligibility is confirmed the research coordinator and/or the attending surgeon will initiate the research consent conversation.

2 \* Describe measures that will be implemented to avoid participant coercion or undue influence (if not applicable to the study, enter "N/A").:  
All patients will be assured that their care is standard and will not be affected by their choice to participate. In addition, the outcome of the study will not be revealed to the patient nor their doctor, therefore participation in the study is completely voluntary.

3 \* Who will recruit participants (or acquire charts/records/samples) for this study? (Check all that apply)

PI  
 Study Staff  
 Third Party

3.1 If you are using a third party, specify Third Party Recruiters:

4 Upload any recruitment tools such as screening/telephone scripts and introductory letters (do not upload advertisements here):

Name	Created	Modified Date
There are no items to display		

ID: VIEW4E0BCAA0A6C00  
Name: v2\_Recruitment

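### No research draw is specified for inpatients with suspected infection that is then ruled out, so in the hospital samples acute illness and setting are largely confounded with case status, and no analysis separates them

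*Combined protocol and SAP*

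**What the plan says.** Two places tie hospital sampling to a diagnosis already made. Prospective Samples, item 2, plans up to three research draws "to culture for research purposes during their hospitalization for diagnosed surgical site infection". Study Procedures, item 1, whose text is repeated in Prospective Samples, describes the source of participants this way: "Patients will be identified at random in the orthopaedic trauma clinic and current admitted patients who have been diagnosed with an infection". The additional draws, up to ten, also require infection and run over two years from its clinical diagnosis.

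Two other places are wider. Recruitment, item 1, states: "Patients over the age of 18 admitted directly from the orthopaedic trauma clinic will be eligible", with no infection condition in that sentence. Inclusion criterion 1 under Eligibility accepts "Previous fracture fixation with an implant (intramedullary nail, plate, screws), or joint revisions, or periprosthetic fracture" without limiting the setting. It then lists "admitted from orthopaedic trauma clinic due to infection, or inpatient with a known infection" as further routes, so admission because of infection stands apart from infection that is known.

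Study Procedures, item 2, shows that a suspected group exists. Under standard care, for "any patient readmitted to the hospital for suspected surgical site infection cultures are obtained and sent for laboratory analysis". No research draw is attached to that work-up, and no group of suspected-but-ruled-out patients is defined.

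The assay readout may be bacterial colonization or an immune response used as a proxy for biofilm (Sample Collection/Analysis, item 4). The planned analysis is descriptive statistics, t-tests and other methods as appropriate (Sample Size and Data Analysis, item 2), plus correlation of laboratory with clinical findings (Study Procedures, item 1).

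**The concern.** An immune readout may respond to acute illness, whatever its cause. To tell a biofilm signal from an illness signal, the study needs patients who are as ill as the cases, in the same setting, but not infected. Patients worked up for suspected infection and cleared are the natural source. If they are not sampled during the admission, no later analysis can recover that comparison.

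Under the narrower sections, hospital samples come mainly from cases and uninfected samples mainly from clinic. Specificity is then tested mostly in patients who do not resemble the cases. An assay carrying no information on biofilm could still appear to validate, provided the hospital case samples are pooled against clinic non-cases. Nothing in the analysis section prevents that pooling or stratifies by setting.

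Timing adds a second problem. Study Procedures, item 2, places the assay ahead of any current testing, yet hospital draws triggered by a diagnosis come after the event the assay is meant to precede. Those samples cannot show early detection.

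**Working it through.** **Plan's own figure.** The only relevant figure is the anticipated enrolment of 1000-1200. No error rate, power, infection rate or accuracy target accompanies it, so there is nothing to reproduce. The check below concerns the sampling structure.

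**Sections side by side**

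| Section | Inpatients covered | Infection condition |
|---|---|---|
| Prospective Samples, item 2 | those given the in-hospital draws | diagnosed infection |
| Study Procedures, item 1 | current inpatients | diagnosed infection |
| Eligibility, criterion 1 | implant patients in any setting; admitted because of infection; known infection | varies by route |
| Recruitment, item 1 | direct admissions from clinic | none stated |
| Study Procedures, item 2 | readmitted on suspicion | standard-care cultures only; no research draw |

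The eligibility text can admit some uninfected inpatients. The sampling text gives them no specified in-hospital draw. Draws are also due at the initial and each subsequent visit, but the documents do not say whether a hospital admission counts as a visit.

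**Illustration.** Take an assay that reads only acute illness. All four inputs are assumptions:
- a = probability of a positive result in an acutely ill inpatient: 0.60 (range 0.40 to 0.80)
- b = probability of a positive result in a clinic attender: 0.10
- c = share of case samples taken in hospital
- q = share of non-case samples taken from acutely ill inpatients

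Formulas for a single cut-off:
- Sensitivity = c·a + (1 − c)·b
- Specificity = 1 − [q·a + (1 − q)·b]
- AUC = (sensitivity + specificity)/2 = 0.5 + (c − q)(a − b)/2

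With no ruled-out inpatients among the controls (q = 0), specificity is 0.90:

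| c | Sensitivity (a = 0.60) | AUC (a = 0.60) | AUC (a = 0.40) | AUC (a = 0.80) |
|---|---|---|---|---|
| 0.25 | 0.25×0.60 + 0.75×0.10 = 0.225 | 0.5625 | 0.5375 | 0.5875 |
| 0.50 | 0.50×0.60 + 0.50×0.10 = 0.35 | 0.625 | 0.575 | 0.675 |
| 1.00 | 0.60 | 0.75 | 0.65 | 0.85 |

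Among suspected inpatients only (c = q = 1), sensitivity is 0.60, specificity 0.40 and AUC 0.50.

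Two features follow from the last formula:
- The inflation depends on c − q, the imbalance in acute illness between cases and controls. If the wider eligibility routes supply some uninfected inpatients, it shrinks. At c = 1 and a = 0.60, q = 0.10 gives 0.5 + 0.90×0.50/2 = 0.725, and q = 0.25 gives 0.6875.
- Pre-diagnosis clinic draws from later cases, set against clinic controls, have c = q = 0 and AUC 0.50 for this assay. That comparison is not inflated.

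**Precision of a ruled-out stratum.** At an assumed specificity of 0.80, the 95% half-width is 1.96·√(0.80×0.20/n), or about 0.11, 0.08 and 0.06 for n = 50, 100 and 200. The documents give no expected n.

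**The case against.** The strongest reply is that the assay is meant to detect biofilm before clinical signs. For that use, implant patients in clinic who stay uninfected are the right controls, and serial clinic draws before diagnosis are the right case samples. Suspected inpatients answer a different question, namely diagnosis once infection is already suspected. This stands for the early-detection comparison. It does not close the gap, because the analysis section names neither that comparison nor any other as the accuracy analysis.

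A reader might also infer that hospital blood is taken only from diagnosed patients, so that nearly every inpatient sample is a case. The documents do not support that. The sentence in Prospective Samples answers a question about blood volume and does not exclude other inpatient draws. Justification, Objective, & Research Design, item 2, says patients may be infected or not when drawn. The Eligibility and Recruitment sections can bring in uninfected inpatients. Nor are ruled-out patients absent from the study: one recruited in clinic and later cleared in hospital has clinic samples and remains in follow-up. What is missing is a specified draw during that admission.

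The illustration rests wholly on assumptions, and its largest value takes every case sample from hospital. That is why smaller shares are shown.

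Finally, earlier sampling needs earlier consent, and Informed Consent Process, item 6, sets consent in the clinic. That cost is real. However, Privacy of Participants, item 2, already has eligible inpatients approached in their hospital rooms.

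**Conclusion.** The point holds in a limited form. The sections disagree on which inpatients are recruited and drawn, and no research sample is specified for patients whose suspected infection is ruled out. In the hospital samples, acute illness and setting are therefore largely confounded with case status, and the planned analysis does not separate them.

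The harm is conditional: it arises if post-diagnosis inpatient case samples are pooled against clinic non-cases. Under the assumed 60%/10% positivity, the spurious AUC is about 0.56 to 0.75 as the hospital share of case samples goes from 25% to 100%, against 0.50 in suspected inpatients. The true share is not in the documents, so the direction is secure and the size is not. It would be going too far to conclude that the whole validation is compromised, because a comparison restricted to pre-diagnosis clinic draws escapes this problem. The change should be made because it is cheap and the missing samples cannot be obtained afterwards.

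**What to change.** 1. Reconcile Study Procedures, item 1, and Prospective Samples, item 2, with Eligibility and Recruitment, so that one statement says which inpatients are recruited and which are drawn. State whether an admission counts as a visit.
2. Extend the existing in-hospital research draw to consenting eligible patients admitted with suspected infection. Where feasible, take the first research tube when the standard cultures are sent. Stay within the plan's draw and volume limits and the enrolment target of 1200.
3. Keep those whose work-up is negative as uninfected inpatient controls.
4. In Sample Size and Data Analysis, item 2, name pre-diagnosis samples as the primary accuracy set for early detection. Analyse post-diagnosis hospital samples separately. Report specificity by setting: ruled-out inpatients and clinic attenders.

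Cost: wording changes, an added reporting stratum, and consent sought earlier in the admission, which needs staff at that point. Some draws will go to patients who prove uninfected. The number of ruled-out patients is unknown, and so is the precision of that stratum; it should be reported with its confidence interval. Assay results stay blinded from treating surgeons under Sharing of Results, so care is unaffected.

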## Lay Summary

1 \* Provide a summary of the background and purpose of the study in language that can be understood by a person without a medical degree.

Surgical site infection in the orthopaedic surgery population is a significant public health issue. Wound infections result in both increased length of hospital stay and total cost of care.

Surgical site infection (SSI) is the most common preventable adverse outcome after a major operation. The economic costs to the US healthcare system are enormous estimated to be in excess of \$1.8 billion per year. For patients who develop an SSI, the cost may be even higher with length of stay and risk of death doubled. Thus the benefits of any intervention decreasing the risk of SSI are very tangible.

A biofilm is a layer of bacteria that adheres to a surface; in Orthopaedics, this often means adherence to implanted metal after fracture surgery. The test that has been designed by one of the investigators on the study has been shown in an animal model to detect the formation of a biofilm up to 1 month prior to clinical detection. Having a blood assay such as this would allow earlier antibiotics and potentially prevent the need for further surgeries to remove metal implants and clean out the biofilm.

ID: VIEW4E02805CF7000  
Name: v2\_Lay Summary

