## Justification, Objective, & Research Design

**If you uploaded a separate research protocol document in the 'Research Protocol' page, cite the applicable section and page numbers from that document in the answer boxes below.**

1 \* Describe the purpose, specific aims, or objectives of this research. State the hypothesis to be tested:

To determine if a new assay to detect early biofilm colonization can be validated in acute postoperative wound infections in orthopaedic trauma patients who have sustained high energy open/closed lower extremity fractures. This would potentially help decrease the amount of surgical interventions needed for infections as it could allow for early intervention and antibiotics.

2 \* Discuss the research design including but not limited to such issues as: probability of group assignment, potential for subject to be randomized to placebo group, use of control subjects, etc.:

A prospective trial conducted at Shock Trauma of patients between 18 years of age and older who have sustained a fracture with metal implanted. We will be collecting between 1-3 routine blood draws for the purpose of laboratory analysis to assess biofilm growth. Patients may be infected or non-infected at the time of blood draw; they will be selected at random for purposes of this study. All patients will be followed as standard of care by their treating physician for all their follow up visits.

3 \* Describe the relevant prior experience and gaps in current knowledge. Describe any relevant preliminary data:

Surgical site infection in the orthopaedic surgery population is a significant public health issue. Wound infections result in both increased length of hospital stay and total cost of care. Specifically, a biofilm assay would help identify early infection in patients and potentially reduce the need for re-operations for infections as it would allow early antibiotic delivery to the affected areas. Our bacteria of focus would be Methicillin-resistant Staphylococcus aureus (MRSA), as this is one of the most predominant organisms in orthopaedic surgical site infections, but can be included to other pathogens causing surgical site infections.

4 \* Provide the scientific or scholarly background, rationale, and significance of the research and how it will add to existing knowledge:

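### With one code per patient the laboratory can count a patient's tubes, and that count is informative about infection because extra draws are tied to infection and assay readers are not masked

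*Combined protocol and SAP*

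**What the plan says.** **Label.** Prospective Samples, item 4: "Unique code for each patient such that the samples will be blinded from obvious patient identifiers".

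**Draws.** Three accounts are given.
- Justification, Objective, & Research Design, item 2, gives a small number for participants in general: "We will be collecting between 1-3 routine blood draws for the purpose of laboratory analysis to assess biofilm growth".
- Study Procedures, item 1, sets no number: "Blood draws will be taken at the initial and each subsequent visit and will be analyzed in the laboratory of one of the investigators". Prospective Samples, item 2, repeats this, and Research Related Risks, item 1, adds that a vial is taken at a visit even when no other blood work is due.
- Prospective Samples, item 2, also plans up to three research draws during admission for a diagnosed surgical site infection.

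**Extra draws.** Study Procedures, item 1, makes these conditional: "If the patient is currently infected currently, or become infected at any point in the future, additional blood draws may be taken". The limit on them is ten, within two years of diagnosis. A ceiling on frequency is also set: "collection may not occur more frequently than 2 times per week".

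**Who reads the samples.** Resources, item 1, and Study Procedures place the analysis in a study investigator's laboratory. The Lay Summary describes the assay as "The test that has been designed by one of the investigators on the study".

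**Blinding.** Sharing of Results keeps assay data from the treating surgeons. Privacy of Participants, item 1, keeps the log that matches codes to names with clinic staff.

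**The concern.** The stated aim is to validate a new assay against clinical infection. That requires the assay to be read without knowledge of the outcome. Keeping results from the surgeons protects the clinical diagnosis from the assay. Nothing in the plan protects the assay from the clinical diagnosis.

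A shared code lets the bench see how many tubes a patient has given, and infection is what triggers additional tubes. Sample Collection/Analysis, item 4, describes the readout as culture or immune response standing in for biofilm, with no threshold, reading rule or rule for repeat runs. If any reading or cut-off is settled by someone who can infer infection status, agreement between assay and outcome is inflated. A larger sample does not cure this; it only makes a biased estimate more precise.

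**Working it through.** **The plan's own figure.** The only planning number is enrolment of 1000-1200. It has no alpha, power, effect size or infection rate behind it, so it cannot be reproduced. This point does not depend on it. The question is how much the number of tubes under one code reveals.

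**Reading A: routine draws limited to 1-3 (Justification, item 2).**
- Uninfected patient: at most 3 tubes.
- Infected patient: up to 3 + 10 = 13 tubes.
- A code with 4 or more tubes can then belong only to an infected patient.

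Illustration with N = 1200. Assume 5-20% infected, of whom 25-90% reach 4 or more tubes. Patients revealed = N × infected share × share reaching 4:
- low: 1200 × 0.05 × 0.25 = 15
- high: 1200 × 0.20 × 0.90 = 216

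A low count is not proof of no infection. At 10% infected with half reaching 4 tubes, 60 of 120 are revealed. Among the remaining codes, (120 − 60)/(1200 − 60) = 0.053 are infected, against 0.10 overall.

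**Reading B: a draw at every visit with no cap (Study Procedures; Prospective Samples; Research Related Risks).** An uninfected patient can now exceed 3 tubes, so the count is only a marker. Its strength is AUC = P(infected count > uninfected count) + ½ P(equal). Assume Poisson counts, with the same mean number of routine draws in both groups and extra draws added in the infected group:

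| Mean routine draws | Mean extra draws if infected | AUC of tube count |
|---|---|---|
| 3 | 2 | 0.758 |
| 3 | 5 | 0.937 |
| 5 | 2 | 0.717 |
| 5 | 5 | 0.903 |

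Extra draws are optional. If only half of infected patients followed these patterns and the rest looked like uninfected patients, the AUC would be 0.5 × AUC + 0.5 × 0.5. The range becomes 0.5 × 0.717 + 0.25 = 0.61 to 0.5 × 0.937 + 0.25 = 0.72. The signal weakens but does not vanish.

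**Which tubes are exposed.**
- Pre-diagnosis tube read on arrival: not exposed, because no extra draws exist yet.
- Tube read after extra draws have begun: exposed.
- Earlier tube kept in the laboratory freezer (Prospective Samples, item 8; Sample Banking) and read or re-run later under the same code: exposed.

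The plan gives no reading time, so the split among these cases is unknown.

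**Size of bias.** Suppose a share b of readings is borderline and would otherwise be called 50/50, and status is known for a share q of infected readings. Sensitivity then rises by b × q / 2. Neither b nor q is in the documents. With b = 5-20% and q = 25-90%, the rise runs from 0.05 × 0.25 / 2 = 0.6 points to 0.20 × 0.90 / 2 = 9 points. That range only shows that the documents do not determine the size.

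**With one code per tube.** Every code has exactly one tube, so the count carries no information and its AUC is 0.5.

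**The case against.** The strongest reply is that the plan already codes its samples and keeps the name log in the clinic, that extra draws are optional, and that the tubes most relevant to early detection precede diagnosis. Much of this stands, and it limits the point. Several stronger readings are tempting, and the documents do not support them.

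- **Any code with 4 or more tubes is an infected patient.** This holds only under the 1-3 draw account. Three other places draw everyone at every visit with no cap.
- **Twice-weekly spacing marks infected patients.** That figure is a general ceiling on collection, not a schedule for infected patients.
- **Every tube is compromised.** Pre-diagnosis tubes read on arrival are not.
- **Sensitivity and specificity rise by about 5 points.** This takes 10% borderline readings, a figure not in the documents, and status known for every patient. A low count leaves status ambiguous, so the same gain in specificity does not follow. The analysis plan names neither measure.
- **The assay's designer reads the samples.** Names are removed, so this cannot be established. The documents show only that a study investigator designed the assay and that a study investigator's laboratory analyses the samples.
- **Bias has occurred.** The documents show exposure to it, no more.

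What the reply does not answer is the mechanism. The laboratory needs no name log to count tubes that share a code, and no section masks it to infection status or draw history.

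**Conclusion.** The point holds as a gap in masking. The label conceals identity but passes outcome information to the laboratory through the number of tubes per code. That information is decisive under one account of the draw schedule and probabilistic under the other. In the probabilistic case the AUC is 0.72 to 0.94, on assumed draw means and Poisson counts, and lower if fewer infected patients give extra samples.

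The exposure covers tubes read after extra draws begin and stored earlier tubes read or re-run later. What is at risk is the correlation of laboratory with clinical findings in Study Procedures, and hence the validation aim. Its extent depends on how much judgement enters the reading or the choice of threshold, which the plan does not describe, so no figure for the bias can be derived. The remedy is cheap and can be made before the data are linked, so the change should be made.

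**What to change.** 1. In Prospective Samples, item 4, replace the per-patient code with a non-sequential random code unique to each tube.
2. Keep the tube-to-patient link in the clinic-held log described in Privacy of Participants, item 1, at least until readouts have been linked to outcomes. Repeated samples can then still be analysed together by patient.
3. State that laboratory readers are masked to infection status and draw history.
4. Lock the readouts before any link to clinical outcomes is made.
5. Where the assay tolerates storage, run tubes in batches that mix patients in random order. The documents do not show that cultures can be held, so batching should not be required for them; per-tube coding works without it.
6. Reconcile the statements on the number of draws in Justification, Study Procedures, Prospective Samples and Research Related Risks.

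**Cost.** Slightly more label and key management for clinic staff, who already hold the log, and some delay where batching is used. No additional patients or visits are needed.
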